16.3 Appendix 3: Modified New York diagnostic criteria for ankylosing spondylitis

Patients with axSpA are classified as having AS, based on the fulfillment of the 1984 modified New York diagnostic criteria ([van der Linden et al 1984](#)).

Clinical criteria for ankylosing spondylitis

- Low back pain and stiffness for more than 3 months that improves with exercise, but is not relieved by rest
- Limitation of motion of the lumbar spine in the sagittal and frontal planes
- Limitation of chest expansion relative to normal values correlated for age and sex

Radiological criterion for ankylosing spondylitis

- Sacroiliitis grade ≥ 2 bilaterally or grade 3–4 unilaterally

Definite AS if the radiological criterion is associated with at least one clinical criterion.

Source: van der Linden S, Valkenburg HA, Cats A (1984) Evaluation of the diagnostic criteria for ankylosing spondylitis - A proposal for modification of the New York criteria. *Arthritis Rheum*; 27:361-8.

16.4 Appendix 4: Definition of sacroiliitis on imaging

Sacroiliitis on magnetic resonance imaging

An MRI will be considered positive for sacroiliitis (active inflammatory lesions, “positive MRI”, MRI+) if the following characteristics are evident ([Sieper et al 2009](#)):

- The presence of definite subchondral bone marrow edema/osteitis highly suggestive of sacroiliitis is mandatory
- The presence of synovitis, capsulitis, or enthesitis only without concomitant subchondral bone marrow edema/osteitis is compatible with sacroiliitis but not sufficient for making a diagnosis of active sacroiliitis
- Amount of signal required: if there is one signal (lesion) only, this should be present on at least two slices. If there is more than one signal on a single slice, one slice may be enough

Sacroiliitis on X-ray

Grading of radiographic sacroiliitis according to the New York diagnostic criteria ([Bennett and Burch 1968](#)):

- Grade 0: normal
- Grade 1: suspicious changes
- Grade 2: minimal abnormality (small localized areas with erosion or sclerosis, without alteration in the joint width)
- Grade 3: unequivocal abnormality - (moderate or advanced sacroiliitis with erosions, evidence of sclerosis, widening, narrowing, or partial ankylosis)
- Grade 4: severe abnormality (total ankylosis)

Sources:

Bennett and Burch (1968) The epidemiological diagnosis of ankylosing spondylitis. Book: Population studies of rheumatic diseases, pp. 305-313

16.5 Appendix 5: Bath Ankylosing Spondylitis Disease Activity Index

The BASDAI consists of a 0 through 10 scale (0 being no problem and 10 being the worst problem, captured as a continuous VAS), which is used to answer 6 questions pertaining to the 5 major symptoms of AS:

1. How would you describe the overall level of **fatigue/tiredness** you have experienced?
2. How would you describe the overall level of **AS neck, back or hip pain** you have had?
3. How would you describe the overall level of pain/swelling in joints other than **neck, back, hips** you have had?
4. How would you describe the overall level of **discomfort** you have had from any areas tender to touch or pressure?
5. How would you describe the overall level of **morning stiffness** you have had **from the time you wake up?**
6. How long does your morning stiffness last from the time you wake up?

To give each symptom equal weighting, the mean (average) of the two scores relating to morning stiffness (questions 5 and 6) is taken. The mean of questions 5 and 6 is added to the scores from questions 1-4. The resulting 0 to 50 score is divided by 5 to give a final 0 – 10 BASDAI score. Scores of 4 or greater suggest suboptimal control of disease, and subjects with scores of 4 or greater are usually good candidates for either a change in their medical therapy or for enrollment in clinical trials evaluating new drug therapies directed at Ankylosing Spondylitis. BASDAI is a quick and simple index (taking between 30 seconds and 2 minutes to complete).

16.6 Appendix 6: Bath Ankylosing Spondylitis Metrology Index

Cervical rotation

Cervical rotation is measured twice with the subject supine on plinth, head in neutral position, forehead horizontal (if necessary, with the head on a pillow or foam block, which must be documented for future reassessments). A goniometer (preferably a gravity goniometer) is placed centrally on the forehead. Subject rotates head as far as possible to the right, keeping shoulders still; ensure no neck flexion or side flexion occurs. The angle between the sagittal plane and the new plane after rotation is recorded. The higher reading of two assessments is recorded in degrees. The same procedure is repeated twice for the left side. Record the mean of the higher reading from the right side and the higher reading from the left side.

Tragus to wall distance

Tragus to wall distance is measured twice with the subject's heels and back rested against the wall. The chin should be at usual carrying level and the subject takes maximal effort to touch the head against the wall. The distance between the tragus and the wall is assessed on each side, and an average of the two distances from each side is calculated. The procedure is repeated, and the shorter of the two average assessments is reported.

Spinal lateral flexion (lumbar lateral flexion)

Subject stands with heels and buttocks touching the wall, knees straight, shoulders back, and hands by the side. The subject bends to the right side as far as possible, without lifting the left foot/heel or flexing the right knee and maintaining a straight posture with heels, buttocks, and shoulders against the wall. The distance from the third fingertip to the floor when subject bends to the side is subtracted from the distance when subject stands upright. The higher of two tries is recorded. The maneuver is repeated on the left side. Record the mean of the larger difference from the right side and the larger difference from the left side.

Lumbar flexion (modified Schoeber index)

Subject is standing erect. Set marks in upright position 5 cm below and 10 cm above lumbosacral junction (spinal section of a line joining the dimples of Venus). Measure the difference between the distance between marks in a standing position (15 cm) vs. a forward flexed position when the subject bends forward as far as possible, keeping the knees straight. The procedure is repeated, and the higher difference of the two tries is reported.

Maximal intermalleolar distance

Subject is lying down with the legs separated as far as possible with knees straight and toes pointing upwards. Alternatively, the subject stands and separates the legs as far as possible. Distance between medial malleoli is measured, and the higher of the two readings is recorded.

Chest expansion

Chest expansion is measured with the subject's hands resting on or behind the head. The measurement is taken at the fourth intercostal level anteriorly. The difference between maximal inspiration and expiration in cm (to the nearest 0.1 cm) is recorded twice, and the higher difference of the two tries is reported.

Occiput-to-wall distance

Occiput to wall distance is measured twice with the subject's heels and back rested against the wall. The chin should be at usual carrying level, and the subject takes maximal effort to touch the head against the wall. The distance between the occiput and the wall is assessed, and the shorter of the two readings is reported.

16.7 Appendix 7: Guidelines for administering the questionnaires for patient reported outcomes

Before study start

Study coordinators should familiarize themselves with the PRO questionnaire(s) in the study and identify any items where a patient's response might highlight issues of potential concern.

For example, one question in the SF-36 asks 'How much of the time in the past 4 weeks- have you felt downhearted and blue?' If a patient responds 'most or all of the time', then the study coordinator should inform the study investigator.

Before completion

1. Subjects should be provided with the correct questionnaire at the appropriate visits and in the appropriate language
2. Subjects should have adequate space and time to complete the forms
3. Questionnaire should be administered before the clinical examination

During completion

1. Administrator may clarify the questions but should not influence the response
2. Only one response for each question
3. Also see "Addressing Problems and Concerns"

After completion

1. Check for completeness and not for content*
2. Check for multiple responses that were made in error

*However, any response which may directly impact or reflect the patient's medical condition (e.g. noting of depression) should be communicated by the study coordinator to the investigator).

Addressing problems and concerns

Occasionally a patient may have concerns or questions about the questionnaires administered. Guidance related to some of the most common concerns and questions are given below.

The patient does not want to complete the questionnaire(s)

Tell the patient that completion of the questionnaire(s) is voluntary. The goal is to better understand the physical, mental and social health problems of patients. Emphasize that such information is as important as any other medical information and that the questionnaire(s) is simple to complete. Suggest that the questionnaire(s) may be different from anything the respondent has filled in the past. If the patient still declines, retrieve the questionnaires. Record the reason for the decline and thank the patient.

The patient is too ill or weak to complete the questionnaire(s)

In these instances, the coordinator may obtain patient responses by reading out loud each question, followed by the corresponding response categories, and entering the patient's response. No help should be provided to the patient by any person other than the designated study coordinator. The coordinator should not influence patient responses. The study coordinator cannot translate the question into simpler language and has to be read verbatim.

The patient wants someone else to complete the questionnaire(s)

In no case should the coordinator or anyone other than the patient provide responses to the questions. Unless specified in the study protocol, proxy data are *not* an acceptable substitute for patient self-report. Patients should be discouraged from asking a family member or friend for help in completing a questionnaire.

The patient does not want to finish completing the questionnaire(s)

If non-completion is a result of the patient having trouble understanding particular items, ask the patient to explain the difficulty. Re-read the question for them *verbatim* but do not rephrase the question. If the respondent is still unable to complete the questionnaire, accept it as incomplete. Thank the patient.

The patient is concerned that someone will look at his/her responses

Emphasize that all responses are to be kept confidential. Point out that their names do not appear anywhere on the questionnaire, so that their results will be linked with an ID number and not their name. Tell the patient that his/her answers will be pooled with other patients' answers and that they will be analyzed as a group rather than as individuals. Tell the patient that completed forms are not routinely shared with treating staff and that their responses will only be seen by you (to check for completeness) and by the investigator. Any response which may directly impact on or reflect their medical condition (e.g. noting of severe depression) will be communicated by the coordinator to the physician.

The patient asks the meaning of a question/item

[figure not shown]
While completing the questionnaire, some patients might ask the meaning of specific items so that they can better understand and respond. If this happens, assist the patient by rereading the question for them *verbatim*. If the patient asks to interpret the meaning of an item, do not try to explain it, but suggest that he/she use his/her own interpretation of the question. Patients should answer the questions based on what *they* think the questions mean.

General information about all questionnaire(s):

All questionnaires have to be completed by the patients in their local languages. The questionnaires should be completed by the patients in a quiet area free from disturbance, and before any visit assessments. Patients should receive no help from family members; if questions cannot be answered alone (due to problems with reading or understanding), then the doctor or nurse should read the questions and record the patient's responses without influencing their answers. The information provided is strictly confidential and will be treated

as such. If a patient has missed a question or given more than one response per question, then this should be brought to patient. Incomplete questions should not be accepted without first encouraging the patient to complete unanswered questions.

The investigator must complete the patient/visit information on the PRO and ensure that the center number, patient's number and initials are identical to the Case Record Form. As there are no source data for this questionnaire, the data queries will be restricted to patient/visit information.

16.9 Appendix 10: Environmental factors related to ASAS Health Index

Environmental factors related to ASAS Health Index

Date: _____

Name: _____

Please answer all statements by placing one check mark per statement to indicate which response best applies to you **at this moment in time** taking into account your rheumatic disease (the term "rheumatic disease" contains all forms of spondyloarthritis including ankylosing spondylitis).

As a result of my rheumatic disease, my family / relatives take more responsibility for household tasks.

I agree

I do not agree

I don't like the way my friends act around me.

I agree

I do not agree

I cannot count on my relatives to help me with my problems.

I agree

I do not agree

I modify my home and work environments.

I agree

I do not agree

I have difficulties getting worsening of my disease acknowledged by a health care professional.

I agree

I do not agree

Treatment of my rheumatic disease is taking up time.

I agree

I do not agree

My friends expect too much of me.

I agree

I do not agree

No one pays much attention to me at home.

I agree

I do not agree

My friends understand me.

I agree

I do not agree

Thank you for answering this questionnaire.

5	Appendix	39
5.1	Imputation rules	39
5.1.1	Study drug	39
5.1.2	AE date imputation	40
5.1.3	Concomitant medication date imputation	42
5.2	AEs coding/grading	43
5.3	Concomitant medication grouping	44
5.4	Laboratory parameters derivations	44
5.5	Clinically notable vital signs	46
5.6	Statistical models	46
5.6.1	SAS code.....	46
5.6.2	Key secondary analysis	48
6	References	48

List of abbreviations

AE	Adverse event
ATC	Anatomical Therapeutic Classification
ASAS	Ankylosing SpondyloArthritis International Society
ASAS-HI	ASAS health index
ASDAS	Ankylosing SpondyloArthritis disease activity score
ASQoL	Ankylosing spondylitis quality of life
AUC	Area Under the Curve
ATC	Anatomical Therapeutic Chemical
ALT	Alanine aminotransferase
AST	Aspartate aminotransferase
axSpA	Axial Spondyloarthritis
BASDAI	Bath ankylosing spondylitis disease activity index
BASFI	Bath ankylosing spondylitis functional index
BASMI	Bath ankylosing spondylitis Metrology Index
bid	bis in diem/twice a day
BSL	Baseline
BMI	Body mass index
CM	Concomitant Medication
CI	Confidence Interval
CRF	Case Report Form
CRP	C-reactive protein
CRO	Contract Research Organization
CSR	Clinical Study report
CTC	Common Toxicity Criteria
CTCAE	Common Terminology Criteria for Adverse Events
DAR	Drug administration record
DMARD(s)	Disease-Modifying Anti-Rheumatic Drug(s)
DMC	Data Monitoring Committee
eCRF	Electronic Case Report Form
ECG	Electrocardiogram
EOT	End of treatment
ENR	Enrolled set
ESR	Erythrocyte sedimentation rate
EudraCT	European Union Drug Regulating Authorities Clinical Trials
FACIT	Functional assessment of chronic illness therapy
FAS	Full Analysis Set
GGT	Gamma-glutamyl transferase
IA	Interim Analysis
ICF	International classification of functioning
IVR	Interactive Voice Response
IWR	Interactive Web Response

MCS	Mental component score
MedDRA	Medical Dictionary for Drug Regulatory Affairs
MMRM	Mixed-Effect Model Repeated Measures
MRI	Magnetic resonance imaging
MTX	Methotrexate
NCI	National Cancer Institute
NSAID	Non-Steroidal Anti-Inflammatory Drug
nr-axSpA	Non-Radiographic Axial Spondyloarthritis
o.d.	Once Daily
OR	Odds Ratio
OS	Overall Survival
PCS	Physical component summary
PDS	Programming Datasets Specifications
PFS	Progression-Free Survival
PK	Pharmacokinetics
PR	Partial remission
PRO	Patient-reported Outcomes
PT	Preferred Term
qd	Quaque die / once a day
QoL	Quality of Life
r-axSpA	Radiographic Axial Spondyloarthritis
RAP	Report and Analysis Process
RECIST	Response Evaluation Criteria in Solid Tumors
SAE	Serious adverse event
SAP	Statistical Analysis Plan
SD	Standard deviation
SF-36	Short form health survey
	
SOC	Standard-of-Care
TFLs	Tables, Figures, Listings
T2T	Treat-to-Target
	
TNF α	Tumor Necrosis Factor Alpha
VAS	Visual Analog Scale
WBCs	White blood cells
WHO	World Health Organization

1 Introduction

This document describes the detailed statistical methodology to be used in the phase IIIb Clinical Study Report (CSR) for the analysis of AScalate study CAIN457HDE01.

[figure not shown]
CSR deliverables (shells for tables, figures, listings) and further programming specifications are described in the Tables, Figures & Listings (TFL) shells and Programming Datasets Specifications (PDS) respectively.

Data will be analyzed by Novartis and/or the designated Contract Research Organization (CRO). Statistical software SAS version 9.4 or higher will be used for generating TFLs. The content of this statistical analysis plan (SAP) is based on the final study protocol (CAIN457HDE01 version 02 dated 17-May-2021). The planned analysis is described in Section 12 of the protocol.

1.1 Study design

This is a randomized, parallel-group, open-label, multicenter study in subjects with active axial spondyloarthritis (axSpA). The aim of the study is to demonstrate that the efficacy of a Treat-to-Target (T2T) approach (with secukinumab as a first-line biologic) is superior to a Standard-of-Care (SOC) approach in terms of achieving strong clinical efficacy in patients with active axSpA who are naïve to biological therapy and who have an inadequate response to prior non-steroidal anti-inflammatory drug (NSAID) treatment. The study will include an 8-week screening period, a 36-week treatment period, and a 20-week safety follow-up period. Neither investigators nor subjects will be blinded. The primary endpoint is the percentage of subjects achieving an Ankylosing SpondyloArthritis International Society (ASAS) 40% response (ASAS40) at Week 24. At Baseline, subjects will be randomized equally to one of 2 treatment groups (T2T or SOC); a total of 300 subjects (150 subjects in each arm) will be randomized as shown in [Figure 1-1](#).

Figure 1-1 Study design

[figure not shown]
Subjects will be evaluated every 12 weeks from Baseline up to Week 36. Safety evaluations will be included in the regular visits; in addition, a safety follow-up visit will be performed 20 weeks after the last study visit (i.e. Week 36) and will take place at Week 56 for subjects completing the study according to the protocol. In addition, subjects in the T2T arm will be seen for safety monitoring at Visit 4 (Week 4) and Visit 5 (Week 8). Subjects who prematurely discontinue completely from the study for any reason should return for the final visit to conduct the Week 36 assessments (4 weeks after the last study treatment administration), then also return after an additional 20 weeks for a final follow-up visit, corresponding to Week 56 assessments.

[figure not shown]
1.2 Study objectives and endpoints

[figure not shown]
Table 1-1 Objectives and related endpoints

Objectives	Endpoints
Primary objective 
To demonstrate that the efficacy of a T2T approach (with secukinumab as first-line biologic) is superior to the SOC approach as measured by percentage of subjects achieving an ASAS40 response at Week 24.	Endpoint for primary objective 
Percentage of subjects achieving an ASAS40 response at Week 24.
Secondary objectives 
To demonstrate that the efficacy of the T2T approach (with secukinumab as first-line biologic) is superior to the SOC approach based on the percentage of subjects achieving an ASAS40 response at Week 12.To demonstrate that the efficacy of the T2T (with secukinumab as first-line biologic) is superior to the SOC approach based on the percentage of subjects achieving an Ankylosing SpondyloArthritis Disease Activity Score (ASDAS) clinically important improvement (defined as change from Baseline (BSL) of ≥ 1.1) at Week 12 and Week 24.To demonstrate that the efficacy of the T2T (with secukinumab as first-line biologic) is superior to the SOC approach based on the percentage of patients achieving an ASDAS major improvement (defined as change from BSL of ≥ 2.0) at Week 12 and Week 24.To demonstrate that the efficacy of the T2T approach (with secukinumab as first-line biologic) is superior to the SOC approach based on the percentage of subjects achieving ASDAS < 1.3 at Week 12 and Week 24.To demonstrate that the efficacy of the T2T approach (with secukinumab as first-line biologic) is superior to the SOC approach based on the percentage of subjects achieving ASDAS < 2.1 (low disease activity) at Week 12 and Week 24.	Endpoints for secondary objectives 
Percentage of subjects achieving an ASAS40 response at Week 12.Percentage of subjects achieving an ASDAS clinically important improvement (defined as change from BSL of ≥ 1.1) at Week 12 and Week 24.Percentage of patients achieving an ASDAS major improvement (defined as change from BSL of ≥ 2.0) at Week 12 and Week 24.Percentage of subjects achieving ASDAS < 1.3 at Week 12 and Week 24.Percentage of subjects achieving ASDAS < 2.1 (low disease activity) at Week 12 and Week 24.

Objectives	Endpoints

• To demonstrate that the efficacy of the T2T approach (with secukinumab as first-line biologic) is superior to the SOC approach based on the percentage of subjects achieving ASAS 20% response (ASAS20), ASAS partial remission (PR), and Bath Ankylosing Spondylitis Disease Activity Index 50% response (BASDAI50) responses at Week 12 and Week 24.• To demonstrate that the T2T approach (with secukinumab as first-line biologic) is superior to the SOC approach in terms of improvement of disease activity, function, axial mobility, and quality of life measures at Week 12 and Week 24 as compared to Baseline according to:
◦ BASDAI◦ ASDAS◦ C-Reactive Protein (CRP) and Erythrocyte Sedimentation Rate (ESR)◦ Bath Ankylosing Spondylitis Functional Index (BASFI)◦ Bath ankylosing spondylitis metrology index (BASMI) and chest expansion◦ Global assessment of disease activity (patient/physician) and general pain on Visual Analog Scale (VAS)◦ ASAS health index (ASAS-HI)◦ Short Form Health Survey (SF-36)◦ Ankylosing Spondylitis Quality of Life (ASQoL)◦ Functional Assessment of Chronic Illness Therapy - Fatigue (FACIT-Fatigue).• To demonstrate overall safety and tolerability of secukinumab.	
• Percentage of subjects achieving ASAS20, ASAS PR, BASDAI50 responses at Week 12 and Week 24.• Improvement of disease activity, function, axial mobility, and quality of life measures at Week 12 and Week 24 as compared to Baseline according to:
◦ BASDAI◦ ASDAS◦ CRP and ESR◦ BASFI◦ BASMI and chest expansion◦ Global assessment of disease activity (patient/physician) and general pain on the VAS◦ ASAS-HI◦ SF-36◦ ASQoL◦ FACIT-Fatigue• The number (and percentage) of patients with treatment-emergent adverse events (AEs).

2 Statistical methods

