1.2 Purpose

[figure not shown]
The purpose of this study is to provide 36-week efficacy data on a T2T approach with secukinumab as first line biologic compared with the standard-of-care (SOC) approach in patients with active axSpA who have an inadequate response to NSAID therapy in order to confirm that such a T2T approach results in superior efficacy compared to the SOC approach, thereby providing an optimal treatment strategy for this patient population.

[figure not shown]
2 Objectives and endpoints

Table 2-1 Objectives and related endpoints

Objectives	Endpoints
Primary objective	Endpoint for primary objective

To demonstrate that the efficacy of a T2T approach (with secukinumab as first-line biologic) is superior to the SOC approach as measured by percentage of patients achieving an ASAS40 response at Week 24.	
Percentage of patients achieving an ASAS40 response at Week 24.
Secondary objectives	Endpoints for secondary objectives

To demonstrate that the efficacy of the T2T approach (with secukinumab as first-line biologic) is superior to the SOC approach based on the percentage of patients achieving an ASAS40 response at Week 12.	
Percentage of patients achieving an ASAS40 response at Week 12.

To demonstrate that the efficacy of the T2T (with secukinumab as first-line biologic) is superior to the SOC approach based on the percentage of patients achieving an ASDAS clinically important improvement (defined as change from BL of ≥ 1.1) at Week 12 and Week 24.	
Percentage of patients achieving an ASDAS clinically important improvement (defined as change from BL of ≥ 1.1) at Week 12 and Week 24.

To demonstrate that the efficacy of the T2T (with secukinumab as first-line biologic) is superior to the SOC approach based on the percentage of patients achieving an ASDAS major improvement (defined as change from BL of ≥ 2.0) at Week 12 and Week 24.	
Percentage of patients achieving an ASDAS major improvement (defined as change from BL of ≥ 2.0) at Week 12 and Week 24.

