2.5.2 Statistical hypothesis, model, and method of analysis

The null hypothesis to be rejected is that the odds of ASAS40 response at Week 24 are equal in both treatment groups. The corresponding alternative hypothesis is that the odds of response at Week 24 are higher under the secukinumab T2T approach compared to a SOC regimen.

Let p_j denote the proportion of ASAS40 responders at 24 weeks for treatment group j , $j=0,1$ where

0 corresponds to the SOC regimen

1 corresponds to the secukinumab T2T regimen

The following hypotheses will be tested:

$H_0: (p_1 / 1-p_1) / (p_0 / 1-p_0) = 1$ vs. $H_A: (p_1 / 1-p_1) / (p_0 / 1-p_0) \neq 1$

In other words:

H_A : The odds ratio (OR) of achieving an ASAS40 response at Week 24 for the comparison of secukinumab T2T vs. SOC is different from 1.

The **primary analysis** will be performed comparing treatments with respect to the primary efficacy variable in a multiple logistic regression model with treatment and center as factors and weight as well as Baseline CRP level as covariates. The adjusted OR, the corresponding 95% confidence interval (CI) and the p-value will be given. The H_0 of equal odds will be rejected if the 2-sided p-value from the logistic regression model for the factor “treatment” is < 0.05 ; however, superiority of secukinumab T2T approach will be claimed only if the direction is correct, i.e. if the odds of response are larger under secukinumab T2T approach.

Tables will also show the number and percentage of patients achieving ASAS40 response.

The primary efficacy analysis will be based on the FAS. The primary analysis will be performed when all subjects have completed the Week 24 assessment.

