2.6 Analysis of the key secondary objective

There are no key secondary objectives in this study.

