2.7.1.2 ASAS20 response

Response at Week 12, Week 24 [REDACTED] to ASAS20 will be will be analyzed analogous to the primary endpoint (see [Section 2.5.1](#) for definition of the ASAS20 responder).

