2.7.2 Statistical hypothesis, model, and method of analysis

Between-treatment comparisons for binary variables in the FAS population (e.g. ASAS20, ASAS40) at individual analysis visits will be evaluated using a logistic regression model with treatment and center as factors and weight as covariates. Odds ratios and 95% CI will be presented for appropriate treatment comparisons. Continuous variables will be evaluated, using a MMRM, with treatment group and analysis visit as factors and Baseline score for related assessment and weight as continuous covariates. Treatment group by analysis visit and Baseline related assessment by analysis visit will be included as interaction terms in the model. An unstructured covariance matrix will be assumed. If covariance matrix will not converge then other covariance structure will be used like compound symmetry, autoregressive structure etc. The treatment effect for the secukinumab T2T regimen at different analysis visits will be determined from the pairwise comparison performed between the 2 treatment groups. The adjusted least square means, point estimate of difference between treatment means, 95% CI for treatment difference and p-value will be presented.

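### The secondary efficacy objectives are framed as demonstrations of T2T superiority on about 41 to 65 comparisons, with no decision rule, error control or nominal label

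*SAP*

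**What the plan says.** The primary endpoint, ASAS40 at Week 24, has a full decision rule. Under SAP 2.5.2 the null hypothesis is "rejected if the 2-sided p-value from the logistic regression model for the factor" treatment is below 0.05, and "superiority of secukinumab T2T approach will be claimed only if the direction is correct". Protocol 12.4.2 gives the same two-sided 0.05 threshold.

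The secondary efficacy objectives use the same confirmatory formula as the primary:

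- SAP Table 1-1, ASAS40 at Week 12: T2T "is superior to the SOC approach based on the percentage of subjects achieving an ASAS40 response at Week 12". Protocol Table 2-1 matches: "is superior to the SOC approach based on the percentage of patients achieving an ASAS40 response at Week 12".
- SAP Table 1-1, continuous measures at Weeks 12 and 24: "To demonstrate that the T2T approach (with secukinumab as first-line biologic) is superior to the SOC approach in terms of improvement of disease activity", followed by function, mobility and quality of life.
- The ASDAS states and improvements, ASAS20, ASAS partial remission and BASDAI50 are worded the same way, each at both visits.

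On analysis, SAP 2.7.1.1 treats ASAS40 at Week 12 like the primary, and SAP 2.7.1.2 has ASAS20 "analyzed analogous to the primary endpoint". SAP 2.7.2 gives odds ratios with 95% CIs for binary endpoints. For continuous endpoints the "point estimate of difference between treatment means, 95% CI for treatment difference and p-value will be presented". SAP 2.6 adds: "There are no key secondary objectives in this study". SAP section 4 records no departure from the protocol's analyses.

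No visible text orders the secondary comparisons, makes them depend on the primary, divides alpha among them or calls them nominal or exploratory. The only mention of multiplicity is a footnote to protocol Table 4-1, about a cited earlier trial.

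**The concern.** An objective written as a demonstration of superiority needs a rule for when it has been met. The primary has one and the secondaries do not. A report that follows the plan could call superiority demonstrated on any secondary endpoint and visit with a favourable interval or p-value, even if ASAS40 at Week 24 fails, and nothing in the plan would contradict it.

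The authors do label analyses when they mean to: SAP 2.2.1 and 2.5.4 describe the subgroup analyses as explored. The secondary endpoints carry no such label, so a reader cannot tell which claims are protected against false positives. At stake is the strength of the secondary conclusions. The primary test is not in question.

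**Working it through.** **1. The plan's own figure.** Inputs (protocol 12.7.1, SAP section 3): 50% vs 30%, alpha 0.05, power 90%, continuity-corrected chi-square, 134 per arm. Taking alpha as two-sided:

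- Uncorrected n = [1.960·√(2·0.4·0.6) + 1.2816·√(0.5·0.5 + 0.3·0.7)]² / 0.2² = (1.3579 + 0.8692)² / 0.04 = 124.0.
- Corrected n = (124.0/4)·[1 + √(1 + 4/(124.0·0.2))]² = 133.8, so 134.

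The stated figure reproduces. Alpha and sidedness for the primary are consistent.

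**2. Counting the secondary comparisons** (SAP Tables 1-1 and 2-2, Weeks 12 and 24 only).

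- Responder endpoints: ASAS40 at Week 12 (1), plus four ASDAS criteria, ASAS20, partial remission and BASDAI50 at two visits (7 × 2 = 14). Total 15.
- Continuous measures with SF-36 counted once: BASDAI, ASDAS, CRP, ESR, BASFI, BASMI, chest expansion, patient global, physician global, general pain, ASAS-HI, SF-36, ASQoL and FACIT-Fatigue. 14 × 2 = 28.
- Sum: 15 + 28 = 43.
- Low end: general pain is in the objectives but not in the visible rows of Table 2-2. Without it, 43 − 2 = 41.
- High end: splitting SF-36 into 8 domains plus PCS and MCS gives 13 + 10 = 23 measures, and 15 + 23 × 2 = 61. Adding PCS and MCS responders at Week 24 only (SAP 2.7.1.13) gives 63. At both visits (Table 2-2) the total is 65.

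**3. Chance of at least one false finding favouring T2T.** Assume each comparison is judged at two-sided 5%, so 2.5% in the T2T direction, and that no secondary effect is real.

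- Independent tests: 1 − (1 − 0.025)^k. For k = 43 this is 1 − 0.975^43 = 0.663.
- Equal correlation ρ: 1 − ∫ φ(u)·Φ[(1.96 − √ρ·u)/√(1 − ρ)]^k du.

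| Comparisons with no true effect | ρ = 0 | ρ = 0.5 | ρ = 0.9 |
|---|---|---|---|
| 15 | 31.6% | 18.1% | 7.2% |
| 41 | 64.6% | 29.1% | 9.2% |
| 43 | 66.3% | 29.7% | 9.3% |
| 65 | 80.7% | 34.8% | 10.2% |

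The documents give no correlations, so ρ is assumed and shown as a range. The row for 15 covers the case where most secondary effects are real and only some measures do not respond. The expected number of false T2T-favouring findings does not depend on ρ: 43 × 0.025 = 1.1.

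**4. What full adjustment would cost.** Bonferroni over 43 tests gives 0.05/43 = 0.00116 per test. For a secondary endpoint with a 50% vs 30% effect and 150 per arm, power (uncorrected chi-square approximation) falls from 94.6% to about 62%.

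**The case against.** The strongest reply is that the plan already separates its tiers in substance. There is one primary endpoint, it is the only one with a power calculation, and the SAP states that there are no key secondary objectives. On that reading the secondaries are supportive, and what is missing is a label.

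Two stronger readings are tempting, and the documents do not support them:

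- *Each secondary endpoint is tested at 5%.* The rejection rule is written only for the primary. For the secondaries the SAP says only what will be presented, and the cross-reference to the primary analysis may carry over the model alone. The 5% level is an inference from the 95% CIs, the p-values and that cross-reference.
- *False superiority claims are likely.* Counting significant results in either direction for 43 tests gives 89% at ρ = 0 and 59% at ρ = 0.5, but those figures include results favouring SOC. A chance above one half of a false T2T-favouring finding needs every secondary effect to be null and the tests to be nearly independent. Neither assumption is natural here. The design assumes a real effect on ASAS40, and several secondaries share its components. Four responder endpoints are cuts or changes of one ASDAS score, which reuses BASDAI items and patient global. Most measures repeat at two visits.

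The count is also soft at the edges. Chest expansion has an MMRM row in Table 2-2 but is only listed under SAP 2.7.1.8. The redacted headings in SAP 2.7 leave it unclear whether the SF-36 domain and responder rows are secondary.

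These points limit the size of the problem but do not remove it. The unredacted objectives say demonstrate, and no sentence makes them supportive. Even the most favourable case shown, 7.2%, is nearly three times 2.5%.

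**Conclusion.** The point holds as a gap between the stated aim and the stated inference. About 41 to 65 secondary comparisons are framed as demonstrations of superiority, and no decision rule, hierarchy, gate, alpha allocation or nominal label governs them. If each were judged at the implied level and no secondary effect were real, the chance of at least one false T2T-favouring finding among 43 comparisons would be about 9% to 66%, with 30% at ρ = 0.5. With only 15 true nulls it would be 7% to 32%. These figures rest on the implied 2.5% directional level and on assumed equal correlations. The chance is materially inflated and uncontrolled, but the documents do not support calling a false claim probable. The primary test keeps its error rate. This is an inexpensive improvement to make before reporting, and it does not undermine the design.

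**What to change.** Add to SAP 2.7.2: *Secondary endpoints are not controlled for multiplicity. Their p-values are nominal and their 95% CIs are unadjusted. Superiority is concluded only for the primary endpoint.* Record the change in SAP section 4. In SAP Table 1-1 reword the secondary efficacy objectives as comparing T2T with SOC, and make the same change in protocol Table 2-1 at the next amendment, since protocol 14.1 requires formal approval for any protocol change.

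No data, patients, models or estimates change. The cost is that superiority on a secondary endpoint can no longer be reported as demonstrated. A gated sequence of a few secondary endpoints could recover some of that, but choosing it late in an open-label trial invites the criticism that the choice was data-driven, so it is not proposed here.
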